## 14.8 Patient Privacy

The Sponsor affirms and upholds the principle of patient confidentiality. Throughout this study, all data provided to the Conformal Medical, Inc. or its designee(s) will only be identified by a study-specific subject identification number.

The investigator agrees that representatives of Conformal Medical, Inc., its designee(s), and regulatory authorities may inspect included patients' records to verify trial data, provide the data are treated as confidential and that the subject's privacy is maintained.

## 15.0 Site and Investigator Selection and Training

### 15.1 Selection of Study Sites and Investigators

The Sponsor will select Investigators who are qualified by training and experience and are legally entitled to perform clinical research and to participate in the investigation of the study device. Sites will be selected based upon review of a recent site assessment questionnaire and the qualifications of the Primary Investigator at the site. Each site will have an interventional cardiologist and a cardiac electrophysiologist willing and able to participate in the study. All participating investigators will be trained to the protocol and study procedures prior to enrolling subjects.

### 15.2 Training of Investigators and Research Staff

#### 15.2.1 General Training Requirements

All Investigators and trial research staff are required to attend Sponsor training sessions, which may be conducted at an Investigator's meeting, a site initiation visit, or another appropriate venue. Training by telephone may take place as required. Training of Investigators/trial personnel will include but is not limited to: the Clinical Investigation Plan (including imaging acquisition protocols), investigational device Instructions for Use, CRF completion, adverse event documentation and reporting requirements, and investigator and trial personnel responsibilities.

#### 15.2.2 Investigator Training Requirements

Comprehensive Investigator training will be conducted to ensure that Investigators have a thorough knowledge of the investigational device Instructions for Use, the proper technique for implantation of the CLAAS device, and the Clinical Investigation Plan.

All participating investigators will receive formal training on the device at the site initiation visit. At a minimum, implanting investigators must receive the following training, unless otherwise noted in site-specific training records:

- CLAAS Device Training (including review of the Instructions for Use)
  - Device preparation, use and handling
  - Device positioning and deployment
  - Device removal and dislodgement
  - Implantation procedure steps and training
  - LAA anatomic measurements
- Clinical Investigation Plan Review
  - General procedural and data collection requirements

#### 15.2.3 Training Documentation

A training log must be maintained at each site that documents the Investigators and research staff who have completed study-specific training, the training modules completed, and the date the training was completed. No trial-related activities (other than those considered standard of care at

the study site) may be performed by investigators or research staff who not completed study-specific training.

## 17.0 Appendices

### 17.1 Appendix A: Definitions

**Adverse Device Effect (ADE)** An adverse device effect is an adverse event related to the use of a medical device. This includes:

- Any adverse event resulting from insufficiencies or inadequacies in the instructions for use, the deployment, the implantation, the installation, the operation, or any malfunction of the medical device
- Any event that is a result of a use error or intentional misuse

All adverse device effects will be assessed using the following:

#### Intensity or Severity

Intensity of an adverse event to be used:

Mild	Awareness of a sign or symptom that does not interfere with the patient's usual activity or is transient, resolved without treatment and with no sequelae.
Moderate	Interferes with the patient's usual activity and/or requires symptomatic treatment.
Severe	Symptom(s) causing severe discomfort and significant impact of the patient's usual activity and requires treatment.

#### Relatedness

Relationship to the study device or procedure:

Not related	The cause of the AE is known, and the event is not related to the study device or procedure.
Unlikely to be related	There is little or no temporal relationship to the study device or procedure, and/or a more likely alternative etiology exists.
Possibly related	There is a reasonable possibility that the event may have been caused by the study device or procedure. The AE has a timely relationship to the study device or procedure(s); however, follows no known pattern of response , and an alternative

	cause seems more likely or there is significant uncertainty about the cause of the event.
Related	A related event has a strong temporal relationship and an alternative cause is unlikely.

## Outcome

The clinical outcome of the AE or SAE will be characterized as follows:

Death	The SAE CRF must be completed for this outcome
Recovered without sequelae	The patient returned to baseline status
Ongoing	Patient did not recover, and symptoms continue
Recovered with sequelae	The patient has recovered but with clinical sequelae from the event
Unknown	The patient outcome is unknown

## Treatment or Action Taken

Action taken after the occurrence of an AE or SAE will be reported as:

Interventional Treatment	Surgical, percutaneous or other procedure
Medical Treatment	Medication dose reduction/interruption or discontinuation, or medication initiated for event
None	No action is taken

Anticipated Serious Adverse Device Effect (ASADE)	An anticipated serious adverse device effect is a serious adverse device effect which by its nature, incidence, severity, or outcome has been identified in the investigational plan or application (including a supplementary plan or application).
--	--

**Bleeding complications** Defined according to the following BARC definitions, and classified as major bleeding (Type 3, 4, or 5) and minor bleeding (Type 2)

Type 0: no bleeding

Type 1: bleeding that is not actionable and does not cause the patient to seek unscheduled performance of studies, hospitalization, or treatment by a healthcare professional; may include episodes leading to self-discontinuation of medical therapy by the patient without consulting a healthcare professional

Type 2: any overt, actionable sign of hemorrhage (e.g., more bleeding than would be expected for a clinical circumstance, including bleeding found by imaging alone) that does not fit the criteria for type 3, 4, or 5 but does meet at least one of the following criteria: (1) requiring nonsurgical, medical intervention by a healthcare professional, (2) leading to hospitalization or increased level of care, or (3) prompting evaluation

Type 3

Type 3a

Over bleeding plus hemoglobin drop of 3 to <5 g/dL\* (provided hemoglobin drop is related to bleed)

Any transfusion with over bleeding

Type 3b

Overt bleeding plus hemoglobin drop  $\geq 5$  g/dL\* (provided hemoglobin drop is related to bleed)

Cardiac tamponade

Bleeding requiring surgical intervention for control (excluding dental/nasal/skin/hemorrhoid)

Bleeding requiring intravenous vasoactive agents

Type 3c

Intracranial hemorrhage (does not include microbleeds or hemorrhagic transformation, does include intraspinal)

Subcategories confirmed by autopsy or imaging or lumbar puncture

Intraocular bleed comprising vision

Type 4: CABG-related bleeding

Perioperative intracranial bleeding within 48 h

Reoperation after closure of sternotomy for the purpose of controlling bleeding

Transfusion of  $\geq 5$  U whole blood or packed red blood cells within a 48-h period (NOTE: cell saver products are not counted)

Chest tube output  $\geq 2$ L within a 24-h period

Type 5: fatal bleeding

Type 5a

Probable fatal bleeding; no autopsy or imaging confirmation but clinically suspicious

Type 5b

Definite fatal bleeding; overt bleeding or autopsy or imaging confirmation

**NOTES:**

Platelet transfusions should be recorded and reported but are not included in these definitions until further information is obtained about the relationship to outcomes. If a CABG-related bleed is not adjudicated as at least a type 3 severity event, it will be classified as not a bleeding event. If a bleeding event occurs with a clear temporal relationship to CABG (i.e., within a 48-h time frame) but does not meet type 4 severity criteria, it will be classified as not a bleeding event.

\* Corrected for transfusion (1 U packed red blood cells or 1 U whole blood = 1 g/dL hemoglobin)

**Cardiac tamponade**

Evidence of a new pericardial effusion associated with hemodynamic instability and clearly related to the LAA closure

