### 5.3 Endpoints

#### 5.3.1 Primary Safety Endpoint

The primary safety endpoint is **freedom from major adverse events**, evaluated at hospital discharge or at 7 days post-procedure (whichever occurs later), and defined as absence of the composite of:

- All-cause mortality
- Ischemic stroke
- Systemic thromboembolism

- Device- or procedure-related adverse events requiring open cardiac surgery or major endovascular intervention\*

\*NOTE: Major endovascular intervention includes pseudoaneurysm repair, arteriovenous fistula repair, and other major endovascular repair. Non-major interventions that are excluded from this endpoint include percutaneous catheter drainage of pericardial effusions, percutaneous retrieval of an embolized device, thrombin injection to treat femoral pseudoaneurysm, and nonsurgical treatments of access site complications.

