#### 5.3.3.1 Secondary Safety Endpoints

5.3.3.1.1 **Major procedure-related complications**, defined as the composite of cardiac perforation, pericardial effusion with tamponade, ischemic stroke, device embolization, and major vascular complications as related to the study device or procedure [evaluated in-hospital]

5.3.3.1.2 **Major safety events**, defined as the composite of all-cause mortality, overt CNS injury (Neuro ARC defined), and major bleeding (BARC Type 3-5)

5.3.3.1.3 **Mortality**, classified as cardiovascular or non-cardiovascular reported cumulatively and individually

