Major procedure-related complications	A composite of cardiac perforation, pericardial effusion with tamponade, ischemic stroke, device embolization, and major vascular complications, adjudicated by the independent Clinical Events Committee as related to the study device or procedure
Major safety events	A composite of all-cause mortality, overt CNS injury, and major bleeding
Mortality	
Classified as cardiovascular (defined as cardiac or vascular) or noncardiovascular according to the following ARC definitions. All deaths are considered cardiac unless an unequivocal noncardiac cause can be established. Specifically, any unexpected death even in patients with coexisting potentially fatal noncardiac disease (e.g., cancer, infection) should be classified as cardiac.
 
 
• Cardiac death: Any death due to proximate cardiac cause (e.g., MI, low-output failure, fatal arrhythmia), unwitnessed death and death of unknown cause, and all procedure-related deaths, including those related to concomitant treatment, will be classified as cardiac death.
 
• Vascular death: Death caused by noncoronary vascular causes, such as cerebrovascular disease, pulmonary embolism, ruptured aortic aneurysm, dissecting aneurysm, or other vascular diseases.
 
 
Noncardiovascular death: Any death not covered by the above definitions, such as death caused by infection, malignancy, sepsis, pulmonary causes, accident, suicide, or trauma.

Myocardial infarction	
Defined according to VARC-2 as:
 
Peri-procedural MI (<math>\leq 72</math> h after the index procedure):
 
 
• New ischemic symptoms (e.g. chest pain or shortness of breath), or new ischemic signs (e.g. ventricular arrhythmias, new or worsening heart failure, new ST-segment changes, hemodynamic instability, new pathological Q waves in at least two contiguous leads, imaging
 

evidence of new loss of viable myocardium or new wall motion abnormality) AND

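### The Appendix A definition of cardiac tamponade builds in a causality test, so an unstable effusion of uncertain cause can be left out of major safety events, a composite with no relatedness condition

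*Combined protocol and SAP*

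**What the plan says.** Appendix A (Section 17.1, identical in Versions A and B) has one entry for cardiac tamponade: "Evidence of a new pericardial effusion associated with hemodynamic instability and clearly related to the LAA closure". It sets no time limit.

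Two secondary safety endpoints use the term.

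- **Major safety events** (Section 5.3.3.1.2) is defined in Appendix A as "A composite of all-cause mortality, overt CNS injury, and major bleeding", where major bleeding means BARC Type 3, 4 or 5. It is assessed in hospital and at 45 days, 6 months and 12 months. Neither the section nor the appendix attaches a relatedness condition. Tamponade enters as a bare item, "Cardiac tamponade", in the Type 3b list, with no pointer to the tamponade entry.
- **Major procedure-related complications** (Section 5.3.3.1.1) is assessed in hospital and lists pericardial effusion with tamponade. Appendix A requires its components to be "adjudicated by the independent Clinical Events Committee as related to the study device or procedure".

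Appendix A also gives a relatedness scale with four grades: not related, unlikely, possibly related and related. The possibly related grade covers events where another cause looks likelier or where the cause is substantially uncertain.

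**The concern.** An event definition should say what happened, and attribution should be a separate step. Here the two are joined: an effusion with hemodynamic instability is called tamponade only if its link to the closure is clear. Clarity of that kind is not a grade on the protocol's own scale, so the adjudicator has no stated threshold for it. An event graded possibly related could hardly meet it.

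The plan treats doubt differently for deaths. Appendix A counts every death as cardiac unless a noncardiac cause is beyond dispute, whereas doubt about a tamponade removes the event.

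At stake is the count in a safety composite that was written without a causality filter, in a study whose data are meant to inform a pivotal trial (Section 4.3). The bias can only run downward. Procedure success, and the split of clinically relevant effusions into those with and without tamponade, use the same term.

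**Working it through.** The plan gives no figure on this point, so there is none to reproduce. The check traces one event through the definitions and then shows scale.

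**Step 1: the event.** Take a new pericardial effusion with hemodynamic instability, graded possibly related, drained by catheter and survived. Assume a hemoglobin drop below 3 g/dL, no transfusion, no intravenous vasoactive agents, no surgery for bleeding and no overt CNS injury. The first two limbs of the tamponade entry are met and the third is not, so under Appendix A this is not a tamponade.

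**Step 2: routes into major safety events.**

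| Route | Device or procedure relatedness required? | Met by this event? |
|---|---|---|
| Death from any cause (including Type 5) | No | No |
| Overt CNS injury | No | No |
| Type 3a: hemoglobin drop of 3 to <5 g/dL | No | No |
| Type 3a: "Any transfusion with over bleeding" | No | No |
| Type 3b: hemoglobin drop of 5 g/dL or more | No | No |
| Type 3b: tamponade | Not in the list; yes if the Appendix A entry governs | Depends on which definition is used |
| Type 3b: surgical control | No | No |
| Type 3b: intravenous vasoactive agents | No | No |
| Type 3c (intracranial, intraocular) and Type 4 (CABG-related) | No | Not applicable |

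The outcome turns on the tamponade row alone. With the Appendix A entry the event is at most Type 2, which the plan classes as minor, and it is outside the composite. With the bare BARC item it counts. The same clinical event has two possible classifications, and the plan does not choose between them.

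**Step 3: major procedure-related complications.** A tamponade must first satisfy the clause to be a tamponade at all, and the committee must then judge it related to the device or procedure. Attribution is applied twice to the same event.

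**Step 4: scale.** The target is N = 20 (Section 10.1). Section 10.3.1 plans counts and percentages with no hypothesis tests, so the exact (Clopper-Pearson) 95% limits below are for scale only. They assume no other event in the composite.

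- Event dropped: 0/20 = 0%. Upper limit = 1 − 0.025^(1/20) = 1 − 0.8316 = 16.8%.
- Event counted: 1/20 = 5%. Upper limit = the p that solves (1 − p)^20 + 20p(1 − p)^19 = 0.025, which is 24.9%. Lower limit = 1 − 0.975^(1/20) = 0.1%.

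The documents give no tamponade rate. For assumed rates of 1%, 2%, 3% and 5%, the chance of at least one tamponade in 20 subjects is 1 − (1 − p)^20 = 18%, 33%, 46% and 64%. These are tamponades of any cause. The share that the clause would remove is unknown.

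**The case against.** The strongest reply is that the link is not written down. The BARC list names tamponade without a causality term and without referring to the tamponade entry, although Appendix A does cross-refer elsewhere, for example from procedure success to device success. A committee could give the BARC item its plain clinical meaning and count the event. This stands as far as it goes: the filter is the natural reading, since the appendix has only one tamponade definition, but it is not the only one. It limits confidence in the effect. It does not remove the defect, because two readings give two counts.

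The gap is also narrow. A patient unstable enough to qualify will often receive a transfusion or vasoactive drugs, or lose 3 g/dL of hemoglobin, and then counts by another route. An event that slips through is still visible: Section 10.3.4 tabulates and lists site-reported adverse events and serious adverse events without a relatedness condition, and an effusion treated by pericardiocentesis is classed as clinically relevant. All of this stands.

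A reader might infer that the clause sets a stricter bar than the committee's own test. The documents do not show that. The top relatedness grade already needs a strong temporal link and an unlikely alternative cause, and nothing says that possibly related is enough for the committee. What can be said is that the clause duplicates the committee's step in undefined terms.

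**Conclusion.** The point holds in limited form. The tamponade definition contains a causality test that major safety events does not have, and BARC 3b does not say whether that definition applies. If it does, a non-fatal unstable effusion of uncertain cause that meets no other Type 3 to 5 criterion is left out. In the procedural composite the clause is redundant. The size is one subject in 20, or 5 percentage points, for each event affected. The expected number of such events cannot be derived from the documents. The endpoints are secondary and descriptive, and no decision threshold depends on them.

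Four stronger readings are tempting and not supported:

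- That the composite as a whole is labelled all-cause. The word qualifies mortality only; what matters is that no relatedness condition is stated.
- That late tamponades are excluded. The definition has no time limit, and effusions from 48 hours onward are a recognised category. Lateness matters only if it makes the cause less clear.
- That a tamponade from transseptal puncture escapes the procedural composite. Cardiac perforation is a separate component there and carries no such clause.
- That the clause affects the primary safety endpoint. That endpoint does not name tamponade. Its exclusion of "percutaneous catheter drainage of pericardial effusions" (Section 5.3.1) applies whatever the effusion is called, and the in-hospital window of the procedural composite is likewise a separate matter.

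**What to change.** In Appendix A, delete the last seven words of the tamponade definition, that is, everything after the word instability. Tamponade is then a new pericardial effusion with hemodynamic instability. Add one sentence to the BARC entry stating that Type 3b tamponade uses this definition with no relatedness condition. Leave attribution to the Clinical Events Committee step already written into major procedure-related complications, and keep recording relatedness and timing on the existing scales.

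The cost is a short wording amendment, with no new data and no change to the schedule. The reported rate may be slightly less favourable. A tamponade that is not hemorrhagic would count under major bleeding, but the bare Type 3b item as listed already allows that.

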**CHA2DS2-VASc Score**

A clinical risk stratification scheme for predicting stroke and thromboembolism in patients with nonvalvular AF, updated from the earlier CHADS2 score. Patients are assigned a score from 0 to 9 by adding the points for each applicable risk factor below to obtain a total score:

Risk Factors	Score
Congestive Heart Failure	1
Hypertension	1
Age $\geq 75$ years	2
Diabetes mellitus	1
Stroke/TIA/thromboembolic event in the past	2
Vascular disease (prior MI, PAD, or aortic plaque)	1
Age 65 to 74 years	1
Sex category (female gender)	1

Closure success	Device success (see definition) followed by successful LAA closure (complete closure or peri-device residual leak $\leq 5$ mm in width on TEE at 45 days post-procedure). NOTE: The primary protocol definition of closure success is at the primary performance endpoint evaluation time point of 45 days; closure success at 6 and 12 months will also be evaluated.
CNS hemorrhage	NeuroARC defined  as any brain, spinal cord, or retinal hemorrhage on the basis of imaging or pathology, not caused by trauma (includes symptomatic intracerebral hemorrhage [Type 1.b], symptomatic subarachnoid hemorrhage [Type 1.c], and covert CNS hemorrhage [Type 2.b])
CNS infarction	NeuroARC defined  as any brain, spinal cord, or retinal infarction on the basis of imaging, pathology, or clinical symptoms persisting for $\geq 24$ h (includes ischemic stroke [Type 1.a], ischemic stroke with hemorrhagic conversion [Type 1.a.H], stroke not otherwise specified [Type 1.d], symptomatic hypoxic-ischemic injury [Type 1.e], covert CNS infarction [Type 2.a], and covert CNS infarction with hemorrhagic conversion [Type 2.a.H])
Composite efficacy	Freedom from the composite of all-cause mortality, all stroke, TIA, and systemic thromboembolism
Covert CNS injury	
Acutely asymptomatic brain or spinal cord injury detected by neuroimaging (NeuroARC Type 2), including:
 
Type 2.a Covert CNS infarction
 
Brain, spinal cord, or retinal cell death attributable to focal or multifocal ischemia, on the basis of neuroimaging or pathological evidence of CNS infarction, without a history of acute neurological symptoms consistent with the lesion location
 
Subtype 2.a.H Covert CNS infarction with hemorrhagic conversion
 
Covert CNS infarction includes hemorrhagic conversions. These should be subclassified as Class A or B when CNS infarction is the primary mechanism and neuroimaging or pathology confirms a hemorrhagic conversion.

Class A (Petechial hemorrhage): Petechiae or confluent petechiae within the infarction or its margins, but without a space-occupying effect

Class B (Confluent hemorrhage): Confluent hemorrhage or hematoma originating from within the infarcted area with space-occupying effect

Type 2.b Covert CNS hemorrhage

Neuroimaging or pathological evidence of CNS hemorrhage within the brain parenchyma, subarachnoid space, ventricular system, spinal cord, or retina on neuroimaging that is not caused by trauma, without a history of acute neurological symptoms consistent with the bleeding location

